1.1 Ketamine

Ketamine is a well-known general anesthetic functioning by N-methyl-D-aspartate (NMDA)-receptor antagonism. Additionally, ketamine has diverse molecular targets and neurophysiological properties which can help in the management of acute and chronic pain, depression, posttraumatic stress disorders, and schizophrenia.⁴

1.1.1 Role of ketamine for anesthesia and analgesia

Ketamine can be used for induction of anesthesia, analgesia and for prevention of inflammation and persistent pain. The drug's analgesic and anti-inflammatory effects are particularly useful in perioperative pain management because it reduces opioid requirements.⁵ The analgesic effect is mediated through NMDA receptors⁶, voltage-gated sodium channels^{7,8}, BK channels⁹, opioid receptors (mu, delta)^{10,11} and gamma-aminobutyric acid (GABA) receptors¹² (Table 1). Unsurprisingly, analgesia requires lower concentrations than general anesthesia.^{13,14} A range of systemic inflammatory response is set in motion by surgical trauma, eliciting complex interaction with numerous inflammatory biomarkers.¹⁵ Ketamine anti-inflammatory potential is elucidated by the reduction of biomarker interleukin-6 (IL-6) in early postoperative period.¹⁶ Ketamine also play an important role in depression management.¹⁷

Ostensibly ketamine should be used widely for improving postoperative pain and outcomes. However this is not the case. The psychologic side-effects are one of the main reasons for its limited use. Emergence reactions are in reported in 10-20% of the patients. Consequentially opioid medications are the commonly used medications in perioperative pain management.

Ketamine may play role in reducing perioperative hypotension which has been associated with increased perioperative morbidity and mortality.^{18,19} Usually hypotension is noted as an unavoidable side-effect of general anesthetics induction drugs like propofol.^{20,21} Inhaled anesthetics and opioids also contribute to hypotension. Etomidate is an alternative induction agent which does not cause hypotension but its use is limited due to assumed adrenal suppression.^{22,23} Ketamine preserves hemodynamics better than commonly used anesthetic induction drug propofol and does not cause adrenal suppression like etomidate. Thus Ketamine seems to be a good induction agent, but again the psychologic side-effects again prevents its common use.

In summary, ketamine is a useful drug for anesthesia and analgesia in surgical patients. Common reasons for use in induction and maintenance of anesthesia is the opioid sparing effects and hemodynamic stability. And the most important reason not to use is the psychologic effects.

1.1.2 Psychologic side-effects of ketamine

The use of ketamine in the perioperative period may lead to psychologic side-effects. But the extent of side-effects from low dose ketamine is not fully characterized. Most information of side-effects comes from chronic pain and psychiatry literature where the dosage and duration of ketamine treatment is much higher. In chronic pain management the use of ketamine is associated with dose-dependent side effects including psychedelic symptoms (hallucinations, memory defects, panic attacks), nausea/vomiting, somnolence, cardiovascular stimulation and, in a minority of patients, hepatotoxicity.²⁴ Usually the dose used is 30 mg/hour for 4-14 days. Blagrove et al reported an increase in dream unpleasantness over the three nights after ketamine use.²⁵ Browdelle et al reported dose-related psychedelic effects in healthy volunteers with the use of ketamine.²⁶ However no amnestic medications were given which are routine in the perioperative setting.

1.2 The role of Lamotrigine

The mechanism of psychologic effects of subanesthetic ketamine remains unclear. Increased dopamine release, effect on the γ -aminobutyric acid (GABA) system, and modulation of the serotonergic system have been suggested as possible mechanisms.²⁷ Lamotrigine, an anticonvulsant which decreases presynaptic glutamate release and widely used for neuropsychiatric illness.²⁸ Lamotrigine augmentation of serotonin reuptake inhibitors is well tolerated in treatment-resistant obsessive-compulsive disorder.²⁹ Lamotrigine may play a role in treating ketamine use disorder.³⁰

A key study was reported at the Society of Neuroscience meeting in 1997 and later published in the Archives of General Psychiatry. It reported that in healthy subjects, 300 mg oral lamotrigine significantly decreased ketamine-induced perceptual abnormalities as assessed by the Clinician-Administered Dissociative States Scale ($P < .001$).³¹ Furthermore lamotrigine increased the immediate mood-elevating effects of ketamine ($P < .05$). The authors concluded that glutamate release-inhibiting drugs may reduce the hyperglutamatergic consequences of NMDA receptor dysfunction which may be implicated in the pathophysiologic processes of neuropsychiatric illnesses.

In another experiment designed to identify the sites of action of ketamine in inducing symptoms and to determine the role of increased glutamate release using the glutamate release inhibitor lamotrigine, the authors concluded that lamotrigine pretreatment prevented many of the signal changes and the symptoms associated with ketamine use. The results of this clinical study were confirmed in a laboratory study published in Science 1998 –“Reversal of Phencyclidine Effects by a Group II Metabotropic Glutamate Receptor Agonist in Rats”.³² The authors noted that “*Group II metabotropic glutamate receptors were targeted to normalize glutamatergic disruptions associated with an animal model of schizophrenia, the phencyclidine model. An agonist of this group of receptors, at a dose that was without effects on spontaneous activity and corticolimbic dopamine neurotransmission, attenuated the disruptive effects of phencyclidine on working memory, stereotypy, locomotion, and cortical glutamate efflux. This behavioral reversal occurred in spite of sustained dopamine hyperactivity.*”

Available evidence therefore supports use of lamotrigine for reducing undesirable psychologic effects of low dose ketamine in the perioperative period. If it in fact does, lamotrigine might broaden use of ketamine for anesthesia and pain management.

2. Specific Aim and Hypothesis

Aim – The aim of this pilot trial is to determine whether lamotrigine reduces psychologic side-effects consequent to low-dose ketamine in surgical patients. This pilot study will confirm the feasibility of a subsequent hypothesis testing study, and provide data to strengthen a sample-size estimate.

Hypothesis - Preoperative treatment with 300 mg lamotrigine reduces psychologic side-effects (measured by four key items of Brief Psychiatric Rating Scale: conceptual disorganization, hallucinatory behavior, suspiciousness, and unusual thought content) in adults given ketamine for non-cardiac surgery.

3. Significance

Ketamine has multiple properties of an ideal anesthetic induction and maintenance agent. The analgesic effects has desirable opioid sparing effects, and the anti-inflammatory properties may help improve outcomes. But its use in perioperative setting is limited, primarily, due to concerns of the psychologic side effect. Lamotrigine can help reduce the undesirable psychologic side-effects of ketamine.

4. Plan of investigation

4.1 Outcomes

1.1.1 Primary outcome

1. Psychologic side-effects measured in PACU (up to 90 minutes after ketamine infusion) by four key items of Brief Psychiatric Rating Scale (BPRS) corresponding to positive symptoms of schizophrenia: conceptual disorganization, hallucinatory behavior, suspiciousness, and unusual thought content. Each symptom is rated 1-7 (1 = not present, 2 = very mild, 3 = mild, 4 = moderate, 5 = moderately severe, 6 = severe, 7 = extremely severe), and, therefore, the total score based on four key items of BPRS will be between 4 (best score) and 28 (worst score).

4.1.2 Secondary outcomes

1. Opioid use in PACU – total IV morphine equivalents
2. Pain score in PACU – numeric rating scale (0-10)
3. Binary outcome postoperative nausea vomiting (PONV) in PACU
4. Postoperative Nursing Progress Record (NPR) records nausea vomiting severity as: 0=none, 1= mild, 2=moderate, 3= severe; analysis will compare two study groups on moderate and severe nausea / vomiting (0 or 1 vs. 2 or 3) in the PACU.

4.1.3 Exploratory outcomes

1. Sedation agitation scale³³ (RASS score) at the time of admission in PACU.
2. Average daily opioid utilization during hospitalization (morphine equivalents).

3. Opioid related side-effects, using the opioid related symptom distress scale (ORSDS) on the first and second postoperative days.^{34,35}

4.2 Trial design

Double blind, randomized (1:1), pilot study.

4.3 Sample size

This pilot study will enroll 50 patients, with 25 randomized to lamotrigine or placebo.

With 50 total patients we will be able to estimate a treatment effect with 95% confidence interval. Variability and treatment effect estimates observed in this pilot study will be used for planning larger trials powered for binary outcomes.

Although not the focus, assuming standard deviation of 2 units (Anand and others, Attention of the Neuropsychiatric effects of Ketamine with Lamotrigine reported the mean \pm SD of 1.5 ± 2 for BPRS outcome), the sample size of N=25 patients per group (N=50 patients total) will provide about 90% power at the 0.05 significance level to detect the difference of 1.9 or larger in units drop between two study groups.

5. Eligibility criteria

Patient undergoing elective abdominal surgery. Specifically, we will enroll surgical inpatients 18-65 yr having noncardiac surgery who require a general anesthesia. We will exclude patients in whom ICU admission is planned preoperatively.

5.1 Inclusion criteria

- 18-65 years of age
- Planned overnight hospital stay
- Planned surgery duration 3-6 hours

5.2 Exclusion criteria

- Pediatric and pregnant patients
- History of seizure
- History of Schizophrenia
- History of unstable angina
- Antiepileptic medications
- History of lamotrigine use

6. Training for rating scales:

a. BPRS ratings: will be conducted by anesthesia fellows. All fellows will be trained on how to do the ratings by co-investigator, [name] (Vice-chair of Research, Center for Behavioral Health). Raters

will also have to pass a quiz used in a large ketamine study being conducted at the Cleveland Clinic to assess understanding regarding the ratings.

6. Protocol

6.1 Patient recruitment

From anesthesia preoperative clinic.

6.2 Randomization and blinding

1:1 randomization without stratification use web-based software (Redcap) before surgery. Allocation will be concealed from the patient, the nurse, the operating room team. Both patient and the operating room team will be blinded to the treatment allocation (double blind).

6.3 Preoperative care

Standard preoperative care as per anesthesia care team. Patient will receive lamotrigine vs. placebo with small sips of water. Lamotrigine reaches peak level 1-4 hours after oral administration. Single dose lamotrigine is safe and is not associated with rash.³⁶

6.4 Intraoperative care

Standard intraoperative care as per the anesthesia care team. All patients will receive Ketamine 1 mg/kg at induction. Ketamine 5mcg/kg/min will be started at induction and stopped at the end of surgery.

6.5 Postoperative care

Standard postoperative care as per PACU team. The psychologic side-effects will be measured using Brief Psychiatric Rating Scale (BPRS)^{37,38} using an online tool(<http://farmacologiaclinica.info/scales/BPRS/>), within 90 minutes of PACU arrival and following morning.

Research fellow will receive standardized training in administering BPRS from [name] using structured material. [name] has used this training for other current research projects.

7. Data analysis

The analysis and reporting of the results will follow the CONSORT guidelines (www.consort-statement.org). The process of patient selection and flow throughout the study will be summarized using a flow-diagram.

We will analyze patients in the treatment group to which they are allocated, according to the intention-to-treat principle. Any patients lost to follow-up will be censored at the time they are lost to follow-up.

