7.1 Statistical plan

First, we compared two randomized groups (lamotrigine vs. placebo) for balance on potentially confounding patients' demographic, baseline and surgical characteristics using univariable summary statistics (mean and standard deviation, median and quartiles, or proportions, as

appropriate) and using absolute standardized difference scores (ASDs). ASDs are defined as the absolute value of the difference between means, mean rankings, or proportions divided by a combined estimate of standard deviation; thus the ASD roughly represents the number of standard deviations the two study groups are apart from one another.

The exploratory outcomes will be summarized by two randomized groups using descriptive summary measures: expressed as mean (standard deviation) or median (interquartile range) for continuous variables and number (percent) for categorical variables. No formal statistical test will be conducted for the exploratory outcomes.

Primary analysis

As for primary analysis, two randomized groups will be compared on the continuous total score based on BPRS four items ranging between 4 (best score) and 28 (worst score). We will estimate the effect of Lamotrigine on reduction psychological side-effects of ketamine infusion using the two-sample Wilcoxon rank sum test and Hodges Lehmann estimation of location shift (along with 95% confidence interval). This method is appropriate since we expect that the outcome will exhibit a skewed distribution. If the incidence of any psychologic effects is very low, meaning that vast majority of the patients will have a score of four (corresponding to no symptoms), we will treat the outcome as binary (no symptoms vs. any symptoms). In this case the chi-square test will be used to compare two randomized groups; the odds ratio along with 95% confidence interval will be reported.

The Type I error for the primary analysis will be kept at 5% level with significance criterion of $P<0.05$.

Secondary analysis

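### A reaction treated in PACU before the BPRS rating can be scored at or near 4 and counted as no symptoms, and the plan neither records nor handles this

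*Combined protocol and SAP*

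**What the plan says.** Section 6.5 describes PACU management only as "Standard postoperative care as per PACU team". The BPRS is to be done "within 90 minutes of PACU arrival and following morning". Section 4.1 (primary outcome, numbered 1.1.1) starts the clock elsewhere: "Psychologic side-effects measured in PACU (up to 90 minutes after ketamine infusion". Neither place says how many PACU ratings are made, whether a rating describes the moment or the period since waking, or whether it precedes any treatment of a reaction.

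On scoring, section 4.1 states that "the total score based on four key items of BPRS will be between 4 (best score) and 28 (worst score". Section 7.1 gives the bottom of that range a meaning in its low-incidence clause: "vast majority of the patients will have a score of four (corresponding to no symptoms". In that event, "we will treat the outcome as binary (no symptoms vs. any symptoms". Otherwise the primary comparison is the "two-sample Wilcoxon rank sum test and Hodges Lehmann estimation of location shift".

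The only handling rules are in section 7: "We will analyze patients in the treatment group to which they are allocated, according to the intention-to-treat principle", plus censoring of patients lost to follow-up. Section 4.1.3 lists a RASS score at PACU admission as exploratory, and section 7.1 says exploratory outcomes are summarized without testing.

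**The concern.** A patient who hallucinates on waking may be given a sedative or antipsychotic by the PACU team and then be rated when calm. The score exists, so this is not missing data and neither handling rule applies. It may nevertheless record as symptom-free a patient who had the event the trial is looking for. Treatment is likely to go to the more marked reactions, which under the trial's hypothesis are commoner on placebo.

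This matters even in a pilot. Section 4.3 says the variability and treatment-effect estimates will be used to plan larger trials powered for binary outcomes. Any-symptom rates from which treated reactions have dropped out would feed directly into that calculation. Section 1.1.1 names psychologic effects as a main reason for ketamine's limited use, so reactions marked enough to be treated are of particular interest.

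**Working it through.** **1. The plan's own figure.** Section 4.3 gives a difference of 1.9, SD 2, 25 per group and alpha 0.05 (taken as two-sided). The noncentrality is 1.9 / (2 × √(2/25)) = 3.36. With 48 df the power is 90.8%, which agrees with the stated figure of about 90%.

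**2. Effect on the mean difference.** Suppose a fraction r of reactions in each arm is treated before rating and reset to 4. Each arm's mean excess over 4 is multiplied by (1 − r), so the expected difference is 1.9 × (1 − r). The documents give no value for r, so it is an assumption. With SD held at 2:

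| r | expected difference | t-test power |
|---|---|---|
| 0 | 1.90 | 91% |
| 10% | 1.71 | 84% |
| 20% | 1.52 | 75% |
| 25% | 1.43 | 69% |

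**3. Binary fallback.** Assumed true any-symptom rates are 40% placebo v 16% lamotrigine, 25 per arm, uncorrected chi-square, exact binomial power. Each rate is multiplied by (1 − r):

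| r in both arms | measured rates | risk difference | risk ratio | power |
|---|---|---|---|---|
| 0 | 40% v 16% | 24 points | 0.40 | 49% |
| 10% | 36% v 14.4% | 21.6 points | 0.40 | 44% |
| 20% | 32% v 12.8% | 19.2 points | 0.40 | 39% |
| 25% | 30% v 12% | 18 points | 0.40 | 36% |

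The odds ratio, which section 7.1 reports, moves a little. At r = 0 it is (0.16/0.84)/(0.40/0.60) = 0.29; at r = 25% it is (0.12/0.88)/(0.30/0.70) = 0.32.

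**4. Wilcoxon test.** A simulation assumed 50% v 25% symptomatic, with mean elevations of 5 v 3 points above the floor. Only reactions at least 4 points above the floor could be treated. With 10–30% of those treated in each arm, power falls from about 65% to 53–34% if treatment resets the score fully to 4. It falls only to about 63–59% if treatment halves the elevation. These figures depend on the assumed score shape and should be read to within a few points.

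**5. Direction.** In a separate skewed-score simulation with no true effect and 30% treated in both arms, the rejection rate was 4.4%, so there is no bias. With a true difference of 1.9 and 50% of lamotrigine but 10% of placebo reactions treated, the difference rose to 2.1. Attenuation therefore needs both a true benefit and treatment that is not clearly more likely on lamotrigine.

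**The case against.** The strongest reply is that the documents contain no rule that scores a treated reaction as 4. Whether the rater scores the moment or the whole period since waking is unstated, and the rater training and cited scale sources might settle it. If the rating covers the whole period, much of the problem goes. That stands, and it makes the undefined reference period the first thing to fix. It does not remove the need for a treatment record. Section 1.1.2 calls amnestic medication routine in the perioperative setting, so recall of an earlier reaction cannot be taken for granted.

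Second, using the observed score regardless of treatment is a legitimate treatment-policy choice and fits the intention-to-treat statement. That also stands, and is why the as-rated Wilcoxon analysis should remain primary. Worst rank as the primary rule would be debatable, and it would leave the Hodges-Lehmann shift without a defined value for those patients.

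Third, agitation is not one of the four rated items. A patient treated for agitation alone can correctly score 4 and should not be reclassified.

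Fourth, power is not the focus of a pilot (section 4.3). That is fair. The more lasting cost is a distorted estimate carried into the next trial.

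**Conclusion.** The gap is real, and nothing in the documents closes it. A patient treated before rating for one of the four symptoms can be counted as symptom-free, and the sponsor would have no record from which to see how often this happened. The score and risk differences are attenuated if lamotrigine works and placebo reactions are at least as likely to be treated. Blinding makes equal treatment plausible, although section 6.2 does not name the PACU team or the BPRS rater separately.

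Three stronger readings are not supported:

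- **That the comparison is pulled toward no effect in every case.** It is not, as step 5 of the working shows.
- **That power collapses.** A fall from 49% to 13%, with the risk ratio moving from 0.40 to 0.60, needs half of placebo but only a quarter of lamotrigine reactions to be treated and fully reset. That means 0.5 × 40% = 20% of all placebo patients treated before rating. The documents' only incidence figure is 10–20% for emergence reactions (section 1.1.1), and they give no rescue rate.
- **That the loss is large whatever the event rate.** With 20% v 10%, approximate power is only 16% before any rescue and 13% with 25% treated; the odds ratio moves from 0.44 to 0.46.

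The size is therefore unknown: small if treatment is rare or only partly suppresses symptoms, material if around a fifth or more of marked reactions are fully reset.

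**What to change.** PACU care stays as it is. The changes concern measurement and analysis only.

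1. In section 6.5, state that the PACU BPRS covers the period from PACU arrival to the rating. Reconcile the two 90-minute windows in sections 4.1 and 6.5.
2. Record drug, time and reason for any sedative or antipsychotic given in PACU before the rating for one of the four rated symptoms, not for agitation alone.
3. In section 7.1, count such a patient as having any symptoms in the binary analysis.
4. Keep the as-rated Wilcoxon and Hodges-Lehmann analysis as primary. Prespecify a sensitivity analysis giving these patients the worst rank, and report the number treated in each arm.

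The cost is one case report form line and a few sentences. The downsides are small: the binary outcome becomes symptoms or treatment for them, and it relies on PACU staff recording why a drug was given.

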7.1 Statistical plan

First, we compared two randomized groups (lamotrigine vs. placebo) for balance on potentially confounding patients' demographic, baseline and surgical characteristics using univariable summary statistics (mean and standard deviation, median and quartiles, or proportions, as

appropriate) and using absolute standardized difference scores (ASDs). ASDs are defined as the absolute value of the difference between means, mean rankings, or proportions divided by a combined estimate of standard deviation; thus the ASD roughly represents the number of standard deviations the two study groups are apart from one another.

The exploratory outcomes will be summarized by two randomized groups using descriptive summary measures: expressed as mean (standard deviation) or median (interquartile range) for continuous variables and number (percent) for categorical variables. No formal statistical test will be conducted for the exploratory outcomes.

Primary analysis

As for primary analysis, two randomized groups will be compared on the continuous total score based on BPRS four items ranging between 4 (best score) and 28 (worst score). We will estimate the effect of Lamotrigine on reduction psychological side-effects of ketamine infusion using the two-sample Wilcoxon rank sum test and Hodges Lehmann estimation of location shift (along with 95% confidence interval). This method is appropriate since we expect that the outcome will exhibit a skewed distribution. If the incidence of any psychologic effects is very low, meaning that vast majority of the patients will have a score of four (corresponding to no symptoms), we will treat the outcome as binary (no symptoms vs. any symptoms). In this case the chi-square test will be used to compare two randomized groups; the odds ratio along with 95% confidence interval will be reported.

The Type I error for the primary analysis will be kept at 5% level with significance criterion of $P<0.05$.

Secondary analysis

Assuming log-normal distribution of PACU opioid consumption (in IV morphine equivalent), we will evaluate the percent difference in geometric mean IV morphine equivalent dose between the two randomized groups using t-test on the log-transformed data. To evaluate the difference in mean PACU pain scores (in VRS scale) we will first summarize the pain scores (in VRS scale) by computing PACU time weighted average (TWA) pain score for each patient. Then we will use a t-test to assess the exposure effect on the TWA pain scores. Binary PONV outcome will be compared between two study groups using chi-square test.

We used the Bonferroni adjustment for multiple analyses to preserve Type I error at 5% level for the secondary analysis with the significance criterion of 0.017 for each of the secondary outcome (i.e., $0.05 / 3$).

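### Bonferroni for the secondary outcomes is valid, but Holm's step-down procedure keeps the same 5% familywise control and is never less powerful; the number of tests should be stated with it

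*Combined protocol and SAP*

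**What the plan says.** Under Secondary analysis, section 7.1 names three between-group tests:

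- PACU opioid dose, compared "using t-test on the log-transformed data"
- PACU pain: "Then we will use a t-test to assess the exposure effect on the TWA pain scores"
- nausea and vomiting: "Binary PONV outcome will be compared between two study groups using chi-square test"

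On multiplicity it states: "We used the Bonferroni adjustment for multiple analyses to preserve Type I error at 5% level for the secondary analysis". The per-test cut-off is given as 0.017, and the expression 0.05/3 is printed in parentheses beside that rounded figure.

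The primary outcome has its own 5% level, and exploratory outcomes are not formally tested. The familywise statement therefore covers the secondary tests alone.

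Section 4.1.2 lists a fourth secondary outcome, nausea/vomiting severity, with its own planned comparison: "analysis will compare two study groups on moderate and severe nausea / vomiting (0 or 1 vs. 2 or 3) in the PACU". Section 7.1 neither names a test for it nor counts it in the divisor of 3.

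**The concern.** The plan asks for familywise control at 5% over a small set of tests, with 25 patients per arm. Plain Bonferroni holds every P value to 0.05/3, whatever the other tests show. Holm orders the P values and compares the smallest with 0.05/3, the next with 0.05/2 and the last with 0.05, stopping at the first failure. It gives the same guarantee, with no assumption about dependence, and cannot reject less than Bonferroni at 0.05/3.

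What is at stake is power for the second and third secondary findings. The outcomes are all measured in the same PACU stay, so more than one real effect is plausible.

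**Working it through.** **The plan's own figure.** 0.05/3 = 0.016667, which is 0.017 to three decimals. The stated criterion reproduces, and 3 × 0.05/3 = 0.05.

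**Assumptions.** The documents give no effect sizes, correlations or sidedness for the secondary tests. I take three two-sided z tests and, for the main illustration, independence and 80% power per affected outcome at 0.05/3.

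**Power at the Holm cut-offs.** The two-sided critical values at 0.05/3, 0.025 and 0.05 are 2.394, 2.241 and 1.960. For 80% power at the first, the test statistic has mean 2.394 + 0.842 = 3.236. Then:

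- power at 0.025 = Φ(3.236 − 2.241) = 0.840
- power at 0.05 = Φ(3.236 − 1.960) = 0.899

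An affected outcome's P value therefore falls in one of three bands with these probabilities:

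- A (up to 0.05/3): 0.800
- B (0.05/3 to 0.025): 0.040
- C (0.025 to 0.05): 0.059

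For an unaffected outcome the probabilities are 0.0167, 0.0083 and 0.025.

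**When Holm rejects a given outcome.** Always in band A. In band B, if at least one other outcome is in A. In band C, if both others are in A or B and at least one is in A.

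- *All three affected:* 0.800 + 0.040 × (1 − 0.2²) + 0.059 × (0.8² + 2 × 0.8 × 0.040) = 0.800 + 0.038 + 0.042 = 0.880.
- *Two affected:* 0.800 + 0.040 × (1 − 0.2 × 0.9833) + 0.059 × (0.8 × 0.0167 + 0.8 × 0.0083 + 0.040 × 0.0167) = 0.800 + 0.032 + 0.001 = 0.833.
- *One affected:* 0.800 + 0.040 × (1 − 0.9833²) + a term below 0.0001 = 0.801. The exact gain is 0.14 points.

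**At least one rejection.** Both procedures begin by comparing the smallest P value with 0.05/3, so this probability is identical. With all three affected it is 1 − 0.2³ = 0.992 either way.

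**Familywise error.** Under the complete null, with independence, it is 1 − (1 − 0.05/3)³ = 0.0492 for both. With two of three affected, the remaining null is falsely rejected with probability 0.0167 under Bonferroni. Under Holm the probability is 0.0167 + 0.0083 × 0.96 + 0.025 × 0.704 = 0.042.

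**Sensitivity to the assumed effects.** One million simulated trials per scenario, 25 per arm, gave these per-outcome powers:

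| Affected outcomes and effect | Correlation | Bonferroni | Holm |
|---|---|---|---|
| Three, 0.8 SD | 0 | 66.8% | 76.0% |
| Three, 0.8 SD | 0.5 | 66.8% | 74.5% |
| Two, 0.8 SD | 0 | 66.8% | 70.5% |
| One, 0.8 SD | 0 | 66.8% | 66.9% |
| Three, 0.5 SD | 0 to 0.5 | 26.6% | 30% to 31% |

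In the 80% illustration, correlation 0.3 lowers the three-affected Holm figure from 88% to 87%.

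**The case against.** The strongest reply is that Bonferroni is a correct, prespecified method that does what section 7.1 says it does, and that this is a pilot. Section 2 gives its purpose as feasibility and planning data, and section 4.3 stresses estimation with a confidence interval. All of that stands, and it is why the point is an improvement and not a defect.

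The gain also needs large effects to look large. With 25 per arm, 80% power at 0.05/3 requires 3.236/√12.5 = 0.92 SD on every affected outcome. At 0.5 SD the gain is 3 to 5 points. Nor is Holm free of cost. The extra power comes with more false rejections when some nulls are false, within the 5% bound. Bonferroni's easy matching simultaneous intervals are also lost, though section 7.1 plans none for the secondary outcomes.

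Three stronger readings are tempting, and the documents do not support them.

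- *The plan exceeds 5% because 3 × 0.017 = 0.051.* The exact 0.05/3 is printed beside 0.017, so this is rounding. It could matter only for a P value between 0.01667 and 0.017. Even taken literally, 0.051 is an upper bound: the figure is 0.0501 for independent tests and 0.0482 at correlation 0.3.
- *Holm makes a secondary finding more likely.* It does not change the chance of at least one rejection. In the 80% illustration the chance of rejecting all three rises from 51% to 72%, but the documents have no success rule that requires all three.
- *Four tests will be run at 0.05/3.* That would put the bound at 4 × 0.05/3 = 0.067. Section 7.1 names only three tests, so the documents leave the status of the fourth comparison open and do not establish a breach.

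**Conclusion.** The point holds as a low-severity, nearly free efficiency improvement. That Holm has the same familywise bound and is never less powerful than Bonferroni at 0.05/3 is a mathematical fact and needs no assumption.

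The size does rest on assumptions: three two-sided z tests, independence, and 80% power each at 0.05/3. On those terms the gain is about 8 points per outcome when all three are affected, 3 points when two are, and next to nothing when one is. At smaller effects the gain is more modest. No conclusion of the trial is invalid if Bonferroni is kept.

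**What to change.** Replace the Bonferroni sentence in section 7.1 with:

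> Secondary outcomes are tested with Holm's step-down procedure at familywise 0.05 (0.05/m, 0.05/(m−1), ..., 0.05), and adjusted P values are reported.

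State m explicitly in the same edit:

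- m = 3 if only the opioid, pain and binary PONV tests are done. The cut-offs are 0.05/3, 0.05/2 and 0.05. Say then that the severity outcome in section 4.1.2 is not formally tested.
- m = 4 if the moderate or severe nausea/vomiting comparison is also tested. The cut-offs are 0.05/4 = 0.0125, 0.05/3, 0.05/2 and 0.05. Name its test.

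Write the cut-offs as exact fractions.

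The cost is one or two SAP sentences, with no new data and no design change. The false-rejection risk when some nulls are false rises within 5% (for example from 1.7% to 4.2% with two of three affected). If simultaneous intervals for the secondary outcomes were added later, they would need separate thought.
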